**Table 2 Data Collection per Visit**

Case Report Form	Eligibility/ Baseline Visit	Return Visits	Retrospective Visits (optional)	Final Visit c
Written informed consent/assent	X	--	--	--
Inclusion/exclusion criteria	X	--	--	--

PFIZER CONFIDENTIAL

Case Report Form	Eligibility/ Baseline Visit	Return Visits	Retrospective Visits (optional)	Final Visit c
Patient demographics date of birth, gender, ethnic origin	X	--	--	--
Clinical trial and compassionate use program participation (log format)	X	X	X	
TTR data genetic test results, tissue biopsy	X	--	--	--
Family history of ATTR amyloidosis	X	--	--	--
Medical history past and current signs, symptoms and medical diagnoses	X	--	--	--
Annual updated medical assessment current signs and symptoms	--	X	--	X
General exam weight/height, vital signs, CCI [REDACTED]	X	X	X	X
Concomitant medications (log format) category, indication, start and stop dates	X	X	X	X
Tafamidis treatments (log format) dose, start and stop dates	X	X	X	
Hospitalizations (log format) admission and discharge dates, reason for hospitalization	--	X	X	X
Transplant history and complications (log format) date(s) of transplant(s), organ(s) transplanted, information on complications	X	X	X	X
Adverse events	X	X	X	X
Laboratory data Hematology, clinical chemistry, urinalysis, including glomerular filtration rate [GFR]	X	X	X	X
CCI [REDACTED]	■	■	■	■
[REDACTED]	■	■	■	■
Nerve conduction studies: Upper Extremity, Lower Extremity				
Renal/bladder ultrasound a residual volume, number and size of kidneys, echogenicity	X	X	X	X

Case Report Form	Eligibility/ Baseline Visit	Return Visits	Retrospective Visits (optional)	Final Visit c
Eye examination a intraocular pressure, vitreous, presence of opacities	X	X	X	X
Body composition a total bone mineral density and content, total lean and fat mass	X	X	X	X
CCI [REDACTED]	■	■		X
Patient death b			X	
Patient discontinuation b			X	
Patient status update b			X	

a Printed assessment worksheets will be available to provide to outside specialists performing assessment(s).

b Data on patient deaths, discontinuations, and status assessments will be collected independent of the visit schedule.

c The final visit will be considered as the last recorded visit for the patient/patient while being in THAOS.

Assessments/concomitant medications/status/safety events/labs recorded on this visit will depend on the availability of the data corresponding to a patient/patient at the final visit and will be analysed as appropriate

## 2.2 STUDY OBJECTIVES

The objectives of THAOS are to:

- Describe the population of patients affected with ATTR amyloidoses;
- Enhance the understanding of disease natural history, including the variability and progression of the hereditary and acquired forms of the disease;
- Better understand the genotype – phenotype relationship in ATTRv;
- Compare the progression of disease and overall survival in patients with ATTR amyloidosis with and without liver transplant;
- Foster an international community of medical experts who will develop recommendations on the clinical management of ATTR amyloidoses;
- Provide information to better understand the management and treatment of patients with ATTR amyloidoses through publication of the survey data;
- Provide information on off-label use of tafamidis by identifying patients who do not meet the inclusion criteria for transthyretin amyloid cardiomyopathy (ATTR-CM)
- For tafamidis-treated patients, collect and summarize all AE/SAE data, including for the specific safety concerns outlined in Table 1 Summary of Safety Concerns to be Assessed in THAOS comprising important identified risks, important potential risks, and missing information that includes long-term safety in ATTR-CM patients with **CCI** [REDACTED] Class IV.
- For patients not treated with tafamidis, collect and summarize additional data on the events of interest listed in Table 1.

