## **7.2. Rationale for the Survey**

The Transthyretin Amyloidosis Outcomes Survey (THAOS) is a longitudinal, observational survey open to all patients with TTR gene mutations without a diagnosis of ATTR amyloidosis and to patients diagnosed with ATTR amyloidosis (inclusive of ATTR-PN and ATTR-CM). To date, limited data are available on the natural history of the hereditary (ATTRm) and wild-type (ATTRwt) forms of the disease, including the regional differences in disease expression by TTR variants and non-mutated TTR, and the genotypic-phenotypic relationship in ATTR amyloidosis.

The principal aims of the outcome survey are to better understand and characterize the natural history of the disease by studying a large and heterogeneous patient population. Survey data may be used to develop new treatment guidelines and recommendations, and to inform and educate clinicians about the management of this disease.

The survey can also generate descriptive safety summaries using adverse and serious adverse event (AE/SAE) data in tafamidis-treated participants. All AE/SAE data will be collected and summarized, including (but not limited to) the safety concerns detailed in [Table 1](#), Summary of Safety Concerns to be Assessed in THAOS.

AE/SAE data collection in THAOS will be utilized in the post-marketing setting to provide additional information on the safety of tafamidis over the long term as well as its effect on survival.

Limited data was collected in ATTR-CM studies with tafamidis in patients with New York Heart Association (NYHA) class IV, and it is expected that THAOS will provide additional information on the safety and efficacy of tafamidis in this population. Safety data will be collected through THAOS for all participants treated with tafamidis.

Additional data corresponding to the events of interest detailed in [Table 1 Summary of Safety Concerns to be Assessed in THAOS](#) will also be collected for all THAOS participants (tafamidis-treated and participants not treated with tafamidis). The purpose of the additional data collection is to further characterize the natural history of disease amongst untreated participants and, as applicable, to gather data to provide context for safety events observed amongst tafamidis-treated participants.

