### Assessments

A series of assessments will be used to assess disease progression and the effects of tafamidis treatment including demographics, TTR genetic test results, tissue biopsy results, family disease history, medical history, annual medical assessment, general examination, concomitant medication use, hospitalizations, transplant history and complications related to transplantations, AE/SAE reporting for tafamidis-treated patients, health events of interest, clinical laboratory data, urinalysis, CCI [REDACTED], [REDACTED] neurologic assessments, eye examination, body composition, CCI [REDACTED], [REDACTED] and death.

Data will be collected at an eligibility/baseline visit, return visits, and in the form of status updates if the patient has not visited the site. In addition, pre-baseline retrospective data may optionally be captured.

Return visits will be conducted annually (on average) or at the discretion of the survey physician. The reporting window for collecting changes in signs, symptoms, AEs, and new diagnoses is from the last prior visit.

A final visit, including collection of AE/SAE information will be performed at the completion of the survey or at the time the patient elects to discontinue, whichever occurs first. For patients enrolled in interventional clinical trials that include open-label tafamidis or other open label investigational products, follow-up in THAOS may continue, but AE data collection and reporting will be addressed through the interventional clinical trial sponsor. If a patient dies while enrolled in the survey, the site is asked to collect all available information related to the death.

If a patient enrolls in a double blind investigational clinical trial or any other trial (including Tafamidis Compassionate Use/Early Access Program) during the course of their follow-up in THAOS, data collected for such patients (if included in the THAOS database) will be excluded from analyses specified within this SAP.

AE/SAE data collected in THAOS will be used to further characterize the safety profile of tafamidis and as a result, to fulfil certain aspects of the European Union (EU) post-

marking commitment for tafamidis. Based on the safety concerns detailed in Table 1, corresponding data for Health Events of Interest will be summarized to characterize both the natural history of ATTR amyloidosis in participants not treated with tafamidis and safety concerns amongst tafamidis-treated patients.

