**Table 1 Summary of ongoing tafamidis safety concerns to be addressed in THAOS**

Level of Risk or Missing Information	Specific Concerns
Important potential risks	Hepatotoxicity Reproductive and developmental toxicity and lactation Changes in thyroid function, particularly in pregnant women
Important missing information	Safety and efficacy in patients with ATTR-PN variants other than Val30Met (B3461029 substudy) CCI █ Patients with severe hepatic impairment

Note: The important identified risks (Urinary tract infections, Diarrhea, Upper abdominal pain and Vaginal infections); important potential risks (Hypersensitivity reactions); and missing information (Safety and efficacy in elderly patients and Longer-term safety) have been removed from the list of ongoing safety concerns from the tafamidis EU Risk Management Plan (RMP) Update (v 9.3), approved on 17 February 2020 and therefore will not be addressed in the final clinical study report (CSR) for THAOS.

All AE/SAE data will be collected for patients treated with commercially available tafamidis; patients receiving tafamidis as part of their participation in an open-label clinical study will have AE/SAE data collection through the open-label clinical study; reporting of Health Events of Interest will be available for patients not treated with tafamidis.

All visits are intended to be outpatient visits. Table 2 presents the data collected throughout a patient's participation in THAOS per the case report form (CRF). All assessments listed in Table 2 are recommended, but not required and will be determined by the investigator.

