### Adverse Events & Serious Adverse Events

All adverse events will be coded according to the latest Medical Dictionary for Regulatory Activities (MedDRA) version at the time of analysis.

Adverse events (all causality and treatment-related) will be summarized by severity and starting dose using the tafamidis treated set by phenotype at enrollment and overall, CCI [REDACTED] and either predominantly cardiac or mixed phenotype at enrollment, tafamidis treated set for patients who had severe hepatic impairment at baseline, tafamidis treated set by liver transplantation status (liver transplant prior to first dose of tafamidis/liver transplant after the first dose of tafamidis/no liver transplant).

Separate summaries will be provided for all AEs, treatment related AEs, all SAEs, treatment related SAEs, AEs leading to dose reduction, AEs leading to withdrawal of tafamidis (temporarily or permanently, or delayed) and AEs leading to tafamidis dose interruptions.

Listings will be provided for adverse events corresponding to all enrolled patients and for patients with off-label usage of tafamidis. A separate listing of SAEs will also be provided for tafamidis treated set.

The following AE summary tables will be provided corresponding to some of the important potential risks using the tafamidis treated set.

- For **hepatotoxicity** using the search criteria: MedDRA SMQ (Standardized MedDRA Query) [Broad and narrow] Drug related hepatic disorders – comprehensive search. The derivations and conventions related to the search criteria will follow the programming specifications done in the Periodic Safety Update Report (PSUR) 12 for tafamidis.
- For **reproductive and developmental toxicity and lactation**:
  - MedDRA SMQ (Broad and narrow): Congenital, familial and genetic disorders; Foetal disorders; Neonatal disorders, Neonatal exposures via breast milk.
  - MedDRA Preferred terms (PTs): Exposure during pregnancy, Exposure via father, Foetal exposure during delivery, Foetal exposure during pregnancy, Foetal exposure timing unspecified, Maternal exposure before pregnancy, Maternal exposure during delivery, Maternal exposure during pregnancy, Maternal exposure timing unspecified, Drug exposure before

- pregnancy, Exposure via breastmilk, Maternal drug affecting foetus, Maternal exposure during breastfeeding
- The derivations and conventions related to the search criteria will follow the programming specifications done in the PSUR 12 for tafamidis.

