### Hematology and Chemistry

Change from baseline by yearly intervals of the hematology and biochemistry laboratory parameters will be provided using the tafamidis treated set by starting dose.

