8.2.8 Summary of Analyses

Data	All enrolled	Untreated overall & by phenotype	Untreated predominantly neurologic/mixed	Untreated predominantly cardiac/mixed	Treated Overall and by phenotype	Treated predominantly neurologic/mixed	Treated predominantly cardiac/mixed	Treated by starting dose	[REDACTED]	[REDACTED]	Treated severe hepatic impaired at baseline	Patients not on tafamidis at the time of enrollment with a liver transplant prior to enrollment on THAOS	Patients not on tafamidis at the time of enrollment with a liver transplant after enrollment on THAOS	Patients not on tafamidis at the time of enrollment with no liver transplant	Treated with liver transplant prior to first dose of tafamidis in the study	Treated with liver transplant after first dose of tafamidis in the study	Treated with no liver transplant either prior to first dose of after first of tafamidis in the study	Treated with off-label usage	Untreated predominantly neurologic who become mixed	Untreated predominantly cardiac who become mixed	Treated predominantly neurologic who become mixed	Treated predominantly cardiac who become mixed
Disposition	x	x			x																	
Demography	x	x			x																	
Disease Characteristics	x	x			x																	
Misdiagnoses	x	x			x																	
Ongoing symptoms by A.T.T.R		x			x				x													
relatedness (definite/possibly related/unrelated)																						
Past symptoms by A.T.T.R		x			x																	
relatedness (definite/possibly related/unrelated)																						
New symptoms by A.T.T.R		x			x																	

PFIZER CONFIDENTIAL

CCI				x			x		x			x							x			x	
				x			x		x														
			x			x						x	x	x							x		x
Survival		x			x					x	x	x	x	x	x	x	x						
Exposure to Tafamidis					x			x		x	x				x	x	x						
Concomitant medications		x			x																		
Hospitalizations		x			x					x													
AE/SAE					x			x		x	x				x	x	x	x					
Death	x	x			x					x	x	x	x	x	x	x	x						
Labs – baseline and change from baseline		x			x			x															
Hy's Law					x			x															

Blood pressure – baseline and change from baseline	x	x			x															
ECG				x			x			x								x		x
ECHO				x			x			x								x		x
CCI		x			x															
[REDACTED]			x			x														
[REDACTED]			x			x														
[REDACTED]			x			x														
[REDACTED]				x			x		x									x		x
[REDACTED]				x			x													
Transplant		x			x															
[REDACTED]		x			x															

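### The SAP commits to summarising the Table 1 events of interest in patients not treated with tafamidis, but no visible AE or Table 1 risk table is specified for the untreated set

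*SAP*

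**What the plan says.** The commitment appears three times in the SAP. The objectives (2.2) include: "For patients not treated with tafamidis, collect and summarize additional data on the events of interest listed in Table 1". The Assessments text in 2.1 says that "Health Events of Interest will be summarized to characterize both the natural history of ATTR amyloidosis in participants not treated with tafamidis", alongside safety concerns in treated patients. The paragraph under SAP Table 1 adds that "reporting of Health Events of Interest will be available for patients not treated with tafamidis".

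Protocol section 8 has the same objective. Protocol 7.2 gives two purposes for the extra data: first, to characterise natural history in untreated participants; second, where applicable, "to gather data to provide context for safety events observed amongst tafamidis-treated participants".

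The analysis text narrows the population. Section 8.2.6 introduces the risk-specific tables thus: "The following AE summary tables will be provided corresponding to some of the important potential risks using the tafamidis treated set". The general AE/SAE tables and the exposure-adjusted incidence rates, also in 8.2.6, name the same set. For laboratory data, 8.2.6 says that changes in haematology and "biochemistry laboratory parameters will be provided using the tafamidis treated set by starting dose". The 8.2.8 row "Labs – baseline and change from baseline" nevertheless marks the untreated set as well.

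**The concern.** This is a designated post-authorisation safety study, and the SAP says that its purpose is to support the final study report. If the tables are programmed from the analysis sets named in 8.2.6, the report will hold defined summaries of hepatotoxicity, thyroid and reproductive events for treated patients and none for untreated patients. A stated objective would then be met, at most, by a listing.

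Both protocol purposes suffer. The natural-history description of these events in untreated patients would be missing. So would the context that the protocol hoped, where applicable, to have for events seen on tafamidis.

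**Working it through.** No sample size, power or event figure is involved, and SAP section 4 states that there are no hypotheses. The check traces the objective to each visible output.

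**Step 1: which events are meant.** SAP Table 1 lists three important potential risks: hepatotoxicity; reproductive and developmental toxicity and lactation; and changes in thyroid function. Its note drops the risks removed from the EU risk management plan. The remaining visible entries are patient groups, not events. So three event categories need an untreated summary.

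**Step 2: which outputs cover untreated patients.**

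| Output | Place in SAP | Untreated set summarised? | Counts or rates Table 1 events? |
|---|---|---|---|
| General AE/SAE tables | 8.2.6 | No | Treated only |
| Hepatotoxicity, reproductive/lactation, thyroid tables | 8.2.6 | No | Treated only |
| Exposure-adjusted AE, SAE and mortality rates | 8.2.6, Exposure | No | Treated only |
| AE listing, all enrolled | 8.2.6 | Listed, not summarised | No counts or denominators |
| Hospitalisations | 8.2.6 | Yes | No |
| Deaths | 8.2.6 | Yes | No |
| Survival | 8.2.6 | Yes | No |
| Symptoms after enrolment | 8.2.4 | Yes | No; arranged by severity and TTR relatedness |
| Blood pressure | 8.2.6 | Yes | No |

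Table 1 potential risks with a defined table: treated 3 of 3, untreated 0 of 3.

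**Step 3: the summary grid in 8.2.8.** Eight columns concern untreated or not-on-tafamidis patients: three for the untreated set (overall and by phenotype; neurologic/mixed; cardiac/mixed), three by liver-transplant status and two by change to mixed phenotype (3 + 3 + 2 = 8). The AE/SAE row marks 0 of the 8. Its marks fall under treated overall, treated by starting dose, one redacted column, severe hepatic impairment, the three treated transplant columns and off-label use. No visible row is named for events of interest. Column positions were read from tab spacing in the extracted table.

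**Step 4: can the events be defined without the drug?** Hepatotoxicity and thyroid use MedDRA queries that do not require exposure. The reproductive search is mixed. All 13 of its preferred terms name an exposure or a maternal drug, as does the breast-milk query. The congenital, foetal and neonatal queries describe outcomes and can be applied to untreated patients.

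**Step 5: is a denominator available?** Yes. Section 6.2.1 already follows untreated patients from enrolment to death, start of tafamidis or end of follow-up.

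**Step 6: laboratory data.** The 8.2.6 text names the treated set by starting dose. The 8.2.8 row marks untreated overall, treated overall and treated by starting dose. The grid departs from the text elsewhere too: it marks Disposition for treated and untreated sets, which 8.2.1 confines to all enrolled, and it keeps a Hy's Law row with no matching analysis in 8.2.6. It therefore cannot settle which laboratory instruction governs.

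**The case against.** The strongest reply is that untreated patients are not ignored. Hospitalisations and deaths, which the note at the end of 8.2.6 counts among safety events, are summarised for them, as are survival and symptoms with onset after enrolment. Section 5.4 shows that the gastrointestinal forms carry pre-coded hepatic terms, including hepatotoxicity, so some hepatic events may reach the untreated symptom tables. Section 8.1 also says generally that outcomes are examined in both sets.

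This stands against a broader reading. A reader might infer that untreated patients get no event table at all, or that treated counts will have no background whatever. The documents do not support either. But the reply does not supply the promised summary. The symptom tables do not use the MedDRA searches applied to treated patients, no thyroid or pregnancy term is visible in the section 5.4 list, and 8.1 describes outcomes as clinical, functional and quality-of-life assessments.

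Three further points stand:
- **Redaction.** Section 8.2.7 and some rows and columns of 8.2.8 are blacked out, so an untreated table there cannot be excluded. It is unlikely, because safety endpoints (6.2) and the AE text are visible and refer to none.
- **Ascertainment.** Treated patients on commercial product have all AEs and SAEs collected; for untreated patients the SAP describes reporting of Health Events of Interest. Rates set side by side would not be a fair comparison, and a reader should not infer that an untreated rate would separate drug effect from background.
- **Purpose.** Context for treated events is the protocol's second and conditional purpose. Natural history comes first.

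Finally, this SAP covers the final report only, with separate plans for annual regulatory reporting. That does not help, because the objective is stated in this SAP.

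**Conclusion.** The point holds in a limited form. The SAP commits to a summary of the Table 1 events in patients not treated with tafamidis, and its visible sections specify none: 0 of 3 potential risks, and 0 of 8 relevant columns in the AE/SAE row. What remains is at most an all-enrolled AE listing, and the SAP does not say whether Health Events of Interest in untreated patients enter it. This is a mismatch between objective and analysis sets, not merely missing detail, and it should be corrected.

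No numerical effect can be given, since the documents report neither event counts nor patient-years. The verdict assumes that the redacted parts hold no such table and that the extracted 8.2.8 columns are aligned correctly. It does not rest on any claim about how often hepatic or thyroid events occur in this disease; the documents give no such rate. The laboratory discrepancy is a separate inconsistency. A reader might take the 8.2.8 mark as the correct instruction, but the grid is out of step with the text elsewhere, so only reconciliation is supported.

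**What to change.** 1. In 8.2.6, add one table for the tafamidis untreated set, overall and by phenotype, of the Table 1 events definable without drug exposure: hepatotoxicity, thyroid dysfunction, and reproductive outcomes without the drug-exposure terms. Give patients with events, number of events, patient-years and rate. Keep the SAP's minimum of 10 patients per subgroup for descriptive statistics.
2. Add a matching events-of-interest row to 8.2.8, marked under the untreated overall and by-phenotype column.
3. State how these events are identified in untreated patients: which form, and whether they are MedDRA-coded and searched as in the treated set. SAP Table 2 shows no visible row for Health Events of Interest.
4. Footnote that ascertainment differs (all AEs/SAEs in treated patients, Health Events of Interest in untreated patients), so the rates are descriptive context and not a comparison.
5. Separately, reconcile the laboratory text in 8.2.6 with the Labs row of 8.2.8.

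If the sponsor does not intend the summary, the objective in 2.2 and the text in 2.1 should be revised instead. The cost is small: one table and a short derivation note, from data that the SAP says will be available and person-time that 6.2.1 already defines. The main drawback is that readers may compare the two sets despite the footnote.
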